Brief Description of Study Procedures	
This is a parallel randomized controlled trial. Eligible patients who consent will be randomized to one of two groups: (1) the intervention group who will be given a Dexcom G6 for CGM, or (2) the control group who will follow their current standard finger-prick protocol via a provided Contour Next ONE glucometer. The CGM group must download the Dexcom G6 and Clarity mobile apps for data capture, whereas the standard of care group will use the Contour Next mobile app for their respective readings.
 
The Dexcom G6 captures real-time, dynamic glucose data every five minutes. Devices used in this study are FDA approved and commercially available.

Primary Endpoint	Hemoglobin A1c (HbA1c) level
Secondary Endpoints	Glycemic variability per mean amplitude of glycemic excursion (MAGE), coefficient of variation of HbA1c, range of HbA1c, frequency of hypoglycemic events, healthcare utilization per count of inpatient/outpatient visits, cost of care, current HEDIS performance on diabetes and behavioral health measures, coding specificity for diabetes, emergency department visit per 1000 rate, overall and for patients with diabetes, and hospitalization per 1000 rate related to
	diabetes, and self-reported behavioral changes (e.g. feeling more empowered to self-manage care, engaged with changing healthcare behaviors, and patient perceptions of the technology).
Analysis Population(s)	Patients with diabetes treated at all Reimagine Primary Care facilities (Avenues Internal Medicine, Cottonwood Family Medicine, Cottonwood Senior Clinic, and Holladay Internal Medicine) from 1 November 2018 to 31 December 2019 will be included in this study.
Benefits	Successful demonstration of CGM will allow patients to manage their condition, which may avoid the highs and lows of glucose monitoring and make patients feel better. This may reduce healthcare utilization and cost for the patients and the healthcare system as a whole. Furthermore, general knowledge on how to engage with patients in remote monitoring pilots will be better understood through this study.
Risks	This study includes recruiting patients and data will be collected. To minimize any breach in of private information the team will store data within the enterprise data warehouse/medical record, REDCap, and on secured mobile applications from Contour Next and Dexcom. While all devices used are FDA approved, there could be challenges for new users when using the new Dexcom G6

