- **Hypothesis for Aim 3a:** Greater than 80% of patients who will have been approached to participate in this study will consent to participation.
- **Process for Aim 3a:** The team will record the number of patients approached, consented and those that participate in this study. Metrics will be helpful for estimating future recruitment in other Reimagine Primary Care studies.

Specific Aim 3b: Understand patient satisfaction with CGM

- **Hypothesis for Aim 3b:** Patient’s will be satisfied with CGM device.
- **Process for Aim 3b:** Develop and deploy exit surveys targeting patients randomized to CGM to assess satisfaction with the CGM device and related digital health monitoring services.

Specific Aim 3c: Understand how CGM changed patient behavior

Hypothesis for Aim 3c: Patients will have felt empowered by CGM.

- **Process for Aim 3c:** Within the survey developed/deployed per Aim 3b, include 5-point Likert-based questions soliciting patient opinions and perspectives. Summarize those perspectives so that research investigators and operational leaders can use this information to change clinical operations (as needed).

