3.0 STUDY DESIGN

This is a pilot, parallel randomized controlled trial of CGM versus a standard finger-prick protocol among patients with type I and II diabetes treated at Intermountain Healthcare’s Reimagine Primary Care Clinics. Patients will

be eligible if their most recent HbA1c level is $\geq 6.5\%$ and they are either currently using a glucose meter or are prescribed a glucose meter at their index encounter. Upon consent, which will occur within in a private office/room within the Reimagine Care Clinic, patients will be randomized into one of two groups:

- **Intervention group:** CGM using a Dexcom G6 to measure glycosylated hemoglobin levels every five minutes. Patients will be asked to download the Dexcom G6 and Clarity applications (to have access to their real-time data) and be given a link to complete an exit survey in REDCap near the end of their study participation. Data will be sent via Bluetooth and then exported by the Intermountain research team into a Tableau (or similar) dashboard for data analysis/comparison (**Appendix A**)
- **Control group:** A standard finger-prick protocol that will require patients to continue with their daily fingerprick regimen established by their physician. This group will be given a Contour Next One meter to ensure that each patient is receiving the same level of accuracy by the same device. A review by Ekhlaspour et al of 17 glucose meters demonstrated wide variability, with only two devices achieving the 2013 ISO standard (with the most accurate being the Contour Next) [7]. Patients in the control group will be asked to download the Contour Next application which will send data via Bluetooth similar to above. Data will be aggregated, and protected health information removed prior to analysis (by Intermountain Healthcare and Savvysherpa). At the end of the study, patients will be asked to complete a short survey in REDCap about their willingness to participate in future studies (**Appendix A**).

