12.0 APPENDIX A

This section provides the questions which will be entered into REDCap and patients asked to complete at the end of the CGM study. There will be branching logic used based on the specific group assigned.

- 1. Which group were you assigned to?**
 - a. Group 1 (Dexcom G6)
 - b. Group 2 (ContourNext One)
- 2. What was the main reason that you signed up for this trial? _____.**
- 3. What was your biggest concern when you considered participating in this trial? _____.**
- 4. Were you initially disappointed with your group assignment?**
 - a. Yes
 - b. No

4b. Why were you disappointed with your group assignment? _____.
- 5. (For Group 1 participants): Did the Dexcom G6 impact your glucose management? For example, did it change your diet?**
 - a. Yes
 - b. No
- 6. (For Group 1 participants): Did the Dexcom G6 impact your glucose management? For example, did it change your exercise regimen?**
 - a. Yes
 - b. No
- 7. How did Dexcom G6 impact your glucose management? _____.**
- 8. (For Group 1 and 2 participants): On a scale of 1-5, where 1 is not helpful and 5 is extremely helpful, how would you rate the device?**
- 9. (For Group 1 and 2 participants): On a scale of 1-5, where 1 is extremely poor and 5 is extremely healthy, how would you rate your health BEFORE starting this study?**
- 10. (For Group 1 and 2 participants): On a scale of 1-5, where 1 is extremely poor and 5 was extremely healthy, how would you rate your health AFTER starting this study was completed?**
- 11. (For Group 2 participants): Did the ContourNext One impact your glucose management? For example, did it change your diet?**
- 12. (For Group 2 participants): Did the ContourNext One impact your glucose management? For example, did it change your exercise regimen?**
- 13. How did the ContourNext One impact your glucose management? _____.**
- 14. Did your glucose levels decrease between the initial enrollment and the end of the study? (Suggest inserting this filter question.)**
 - a. They increased
 - b. The decreased

c. No change

15. Would you be willing to participate in future Intermountain pilots in your primary care clinic? a.

Yes

b. No

16. General Comments. In the space provided, please feel free to add any other comments regarding your participation in this study. _____.

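### Aim 3c asks how CGM changed behavior but plans only a summary of CGM-arm survey answers, which cannot separate a CGM effect from features both arms share

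*Combined protocol and SAP*

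**What the plan says.** Section 2.0 of the combined protocol and SAP gives the study a comparative purpose, CGM against standard of care, and names self-reported patient perceptions among the measures of impact. The synopsis lists as a secondary endpoint "self-reported behavioral changes (e.g. feeling more empowered to self-manage care, engaged with changing healthcare behaviors, and patient perceptions of the technology".

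The relevant aim is "Specific Aim 3c: Understand how CGM changed patient behavior", with the hypothesis "Patients will have felt empowered by CGM". The data come from the Aim 3b survey, whose process is "Develop and deploy exit surveys targeting patients randomized to CGM to assess satisfaction with the CGM device". For Aim 3c the protocol adds "Within the survey developed/deployed per Aim 3b, include 5-point Likert-based questions soliciting patient opinions and perspectives", and the analysis is "Summarize those perspectives so that research investigators and operational leaders can use this information to change clinical operations (as needed". Aim 3 as a whole is headed as qualitative. Sections 7.0 and 7.1 specify quantitative analyses for Aims 1 and 2 only.

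Controls are surveyed too. Section 3.3 says both groups complete the end-of-study survey. In Appendix A, items 8 to 10 go to both groups in the same words. Items 5 and 6 ask the CGM arm whether the Dexcom changed diet and exercise. Items 11 and 12 ask controls the parallel questions, for example "Did the ContourNext One impact your glucose management? For example, did it change your diet". Section 3.0 describes the control survey more narrowly: controls are to "complete a short survey in REDCap about their willingness to participate in future studies".

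**The concern.** The aim is worded as an effect of CGM, but its input is the level of answers in one arm. That level also reflects whatever both arms receive: a study-supplied device and app (Sections 3.0 and 3.3), monthly coordinator check-ins (Section 4.2) and resupply contact (Section 3.0). If the two devices prompted similar changes in diet and exercise, the planned summary would not show it.

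The result may be acted on. Section 1.1 calls learning how real-time knowledge influences behavior critical before more sites are added, and Aim 3c says operational leaders can use the summary to change clinical operations as needed. The randomized comparison that would help is largely collected already, yet no section says it will be made.

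**Working it through.** **The plan's own figures.** None is stated for Aim 3c. The only design count is 125 enrolled with 20% attrition: 125 × (1 − 0.20) = 100 analyzed, which reproduces. The documents give no allocation ratio, so 50 per arm is an assumption (1:1, all analyzed patients answering the survey).

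**What each arm is asked (Appendix A).**

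| Topic | CGM arm | Control arm | Match |
|---|---|---|---|
| Device helpfulness, 1–5 | item 8 | item 8 | identical |
| Health before / after, 1–5 | items 9, 10 | items 9, 10 | identical |
| Diet changed | item 5 (Yes/No) | item 11 (no options shown) | parallel, different device named |
| Exercise changed | item 6 (Yes/No) | item 12 (no options shown) | parallel, different device named |
| Empowerment | none | none | not asked |

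The diet and exercise items are also not in the 5-point format that Aim 3c describes.

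**Illustration of a one-arm reading.** Assume no CGM-specific effect, so both arms share a true Yes rate p. Let X ~ Binomial(50, p) be the number of Yes answers in the CGM arm. Two invented rules for a favorable reading are:

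- majority: X ≥ 26;
- stricter: X ≥ 33, the smallest count with exact one-sided p ≤ 0.025 against 50% (P = 0.016 at p = 0.50).

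| Shared p | P(X ≥ 26) | P(X ≥ 33) |
|---|---|---|
| 0.30 | 0.001 | <0.001 |
| 0.40 | 0.057 | <0.001 |
| 0.50 | 0.444 | 0.016 |
| 0.60 | 0.902 | 0.237 |
| 0.70 | 0.998 | 0.782 |
| 0.80 | >0.999 | 0.994 |

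The answer runs from almost never to almost always, depending on a rate and a rule that the documents do not give.

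**What a between-arm contrast offers at 50 per arm.**

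- Proportions: 95% CI half-width = 1.96 × √(2p(1 − p)/50). At p = 0.5 this is 1.96 × √(0.5/50) = 0.196; at p = 0.8 it is 1.96 × √(0.32/50) = 0.157. So it is about 16 to 20 percentage points.
- Item 8 mean rating: half-width = 1.96 × SD × √(2/50) = 0.39 SD. The documents give no SD.
- Two-sided 5% score test: it rejects about 5 to 6% of the time at equal rates of 0.5 to 0.8. Power is about 0.88 for 70% vs 40%, 0.75 for 75% vs 50% and 0.60 for 80% vs 60%.

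The 5% error rate holds only if the Yes rates are equal when behavior is equal. If the device named in the question, or knowledge of assignment, alone moved the rate from 60% to 80%, the same test would reject about 60% of the time. This is why the diet and exercise contrasts can only be supportive.

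**The case against.** The strongest reply is that Aim 3 is qualitative and the trial is described as a pilot. Aim 3c has no test, threshold or effect estimate, and a description of users' perceptions needs no comparator. This stands in part: one-arm description is legitimate if it is read as description. It does not dispose of the point, because the aim's title is causal and Section 2.0 counts self-reported perceptions among the measures of CGM versus standard of care. Aims 1b to 1d are also CGM-only, but the protocol justifies that by their need for near-continuous data. No such reason applies to survey items that controls answer.

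The second reply is that the parallel items are not the same question. Controls continue finger-pricks, and many already use a meter, so asking whether another meter changed their diet differs from asking about a new type of device. With no blinding and possible disappointment at assignment (item 4 asks about it), answers can differ when behavior does not. This stands, and it is why item 8 should lead. Identical wording does not remove expectation bias from item 8 either.

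A reader might go further and infer that the plan will credit CGM with changing behavior even if it does nothing. The documents do not support that. There is no decision rule, the chance depends on an unknown response rate, and leaders can use the summary rather than being committed to it. Nor do the documents support saying that controls answer the same items throughout, or that existing answers could test empowerment.

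The narrower description of the control survey in Section 3.0 is an editorial matter. That sentence cites Appendix A, and Section 3.3 already says both groups are surveyed.

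**Conclusion.** The concern holds in limited form. A causally worded aim serving a listed secondary endpoint rests on a one-arm summary that cannot isolate CGM from what both arms receive. A favorable reading could be reached with no CGM-specific effect. Its frequency cannot be stated from the documents, and the tabulated probabilities are illustrations that assume 50 respondents per arm, Yes/No answers and invented cut-offs.

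The comparator exists exactly for device helpfulness, approximately for diet and exercise, and not at all for empowerment. Even with the contrasts added, the evidence remains unblinded self-report, and only large differences would be visible. The primary analysis and Aims 1 and 2 are unaffected. The change is worth making because it is cheap and the result may inform operations.

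**What to change.** In Aims 3b and 3c, with a matching sentence in Section 7:

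1. Base any statement about CGM's effect on between-arm differences with 95% CIs. Use item 8 as the main contrast, and item 5 vs item 11 (diet) and item 6 vs item 12 (exercise) as supportive contrasts.
2. Confirm Yes/No response options for items 11 and 12.
3. Label these contrasts as unblinded self-report, with device-named stems in the diet and exercise items, and open to expectation bias. State the expected precision.
4. Keep the CGM-only satisfaction and free-text summaries as a description of users' perceptions.
5. For empowerment, either state the hypothesis as CGM users' perception with no causal reading, or add one neutrally worded 5-point item to both arms' surveys.
6. Optionally, align the Section 3.0 description of the control survey with Appendix A.

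The cost is a few sentences. Items 1 to 4 need no new visits, patients or survey questions, provided that items 11 and 12 are fielded with Yes/No options. Only the second option in item 5 adds a question, one per patient. If the contrasts are not wanted, the minimum is to retitle Aim 3c as the perceptions of CGM users.

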3.3 Screening and Selection of Subjects

Subjects will be screened and recruited by Research Coordinators with CITI/HIPAA training. These coordinators will be trained in advance by Drs. [name] and [name], on how to instruct patients of proper usage of their device, how to effectively interact with subjects, the questions that may be posed, how patients should interpret feedback from the devices/cellphones, etc. [name] will also consult with the providers so that they understand the questions that may be asked by the patients and how to provide best care practices.

If a patient agrees to participate, a consent form will be electronically signed using REDCap. Participants will receive a paper copy of the consent containing all relevant and study pertaining information including important contact information. The subject will then be randomized into a study group and given the appropriate device by a Research Coordinator. Each patient will download the mobile apps relevant to their group, so their data can be tracked and transmitted by the study team.

- Group #1 will download the Dexcom G6 and Clarity apps
- Group #2 will download the Contour Next ONE Diabetes application.
- Both groups will also use REDCap to complete the end of study survey (**Appendix A**).

All devices will be registered prior to study startup and will be matched to a deidentified subject identifier (e.g. Subject_001). The coordinators will answer any study related questions that the patients may have before and during the study along with the Reimagine Primary Care clinicians who have agreed to participate as collaborators during the patient's regular appointments. Before patient's leave the clinic, (or ± 2 days) a blood draw will be conducted at the Reimagine site by a certified phlebotomist or approved healthcare provider to collect initial HbA1c level.

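### The Appendix A exit survey has no empowerment item and no item on the digital monitoring services, so the Aim 3c hypothesis has no direct measure and Aim 3b is only partly covered

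*Combined protocol and SAP*

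**What the plan says.** Section 2.0 sets out two survey-based aims that matter here.

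- **Aim 3b** hypothesizes that patients "will be satisfied with CGM device". Its process is an exit survey aimed at the CGM group, covering satisfaction with both the device and the digital monitoring services around it.
- **Aim 3c** is titled as a question about how CGM altered behavior, but its hypothesis is "Patients will have felt empowered by CGM". Its process is to "include 5-point Likert-based questions soliciting patient opinions and perspectives" in the same survey and then summarize the answers for investigators and operational leaders.

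The synopsis (Secondary Endpoints) lists self-reported behavioral changes and gives these as examples: "feeling more empowered to self-manage care, engaged with changing healthcare behaviors, and patient perceptions of the technology".

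The instrument is in Appendix A, which opens: "This section provides the questions which will be entered into REDCap and patients asked to complete at the end of the CGM study". Section 3.3 adds: "Both groups will also use REDCap to complete the end of study survey". Section 5.1 makes finishing the exit survey a condition of completing the study.

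**The concern.** Hypotheses and instrument should match. Aim 3c names a construct (empowerment) and a response format (5-point Likert). Aim 3b names two objects of satisfaction, the device and the services. A reader therefore expects to find at least one item for each in Appendix A, and they are not there.

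Empowerment is not a side issue in this protocol. The purpose statement in Section 2.0 expects CGM to work by empowering patients to manage their diabetes better. If the survey is fielded as printed, the trial will reach its end without a direct observation on that expectation. Answers that were not collected at exit cannot be recovered later as true exit data.

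**Working it through.** No sample size, power or alpha bears on this point. The check is an item-by-item comparison of Appendix A with the aims.

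**Step 1. Sort the 16 numbered questions by content.**

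| Content | Questions | Count |
|---|---|---|
| Group, motives, concerns, disappointment with assignment, future willingness | 1, 2, 3, 4 (with 4b), 15 | 5 |
| Impact of the device on glucose management, with diet or exercise as the example, or open text | 5, 6, 7 (CGM); 11, 12, 13 (control) | 6 |
| 1-5 rating of the device | 8 | 1 |
| 1-5 rating of own health, before and after | 9, 10 | 2 |
| Perceived change in glucose | 14 | 1 |
| General comments | 16 | 1 |

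Check: 5 + 6 + 1 + 2 + 1 + 1 = 16.

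**Step 2. Map each promised construct to the items.**

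| Construct | Where promised | Direct items | Indirect items |
|---|---|---|---|
| Empowerment | Aim 3c hypothesis; example in the synopsis endpoint | 0 of 16 | None that elicits it; 7, 13 and 16 are open text |
| Engagement in changing behaviors | Example in the synopsis endpoint | 0 of 16 | 5-7, 11-13 |
| Satisfaction with the device | Aim 3b | 0 of 16 | 8 |
| Satisfaction with digital services | Aim 3b process | 0 of 16 | None |
| Behavior change | Aim 3c title; synopsis endpoint | Partly: 5-7 (CGM), 11-13 (control) | – |
| Perception of the technology | Example in the synopsis endpoint | Partly: 8 | 7, 13, 16 |

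**Step 3. Check the response format.** Aim 3c calls for 5-point Likert items. Three of the 16 questions use a 1-5 scale: 8, 9 and 10. Questions 9 and 10 rate general health, so only question 8 concerns the device. It is anchored on helpfulness: "where 1 is not helpful and 5 is extremely helpful, how would you rate the device". A device can be helpful and still unsatisfying (skin irritation, alarms or app problems would be examples), so helpfulness is a proxy for satisfaction and says nothing direct about empowerment.

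**Step 4. Check whether the behavior items can stand in.** Questions 5 and 6 are Yes/No. Each asks whether the device affected glucose management and offers diet or exercise only as an example, so a Yes need not mean that diet or exercise changed. They bear on the title of Aim 3c, but not on its hypothesis. Questions 11 and 12 have the same wording for controls; I take them as Yes/No as well, although no response options appear in the text.

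**The case against.** The strongest reply is that the survey is far from empty. Question 8 is a 1-5 device rating from both groups, and it partly serves Aim 3b and perception of the technology. Questions 5-7 and 11-13 address behavior change, which is both the title of Aim 3c and the core of the synopsis endpoint; empowerment and engagement are only examples of that endpoint. Aim 3 is labeled qualitative, so open-text answers count as evidence, and Sections 7.0 and 7.1 place no survey item among the quantitative secondary analyses. All of this stands. It rules out an inference a reader might draw, that Aims 3b and 3c and the self-report endpoint cannot be answered at all or will have no data. It does not supply the missing items: open text may happen to mention empowerment, but no question asks for it, and Aim 3c itself specifies Likert items.

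A second reply is that the survey was not final. Aim 3b speaks of developing it, and question 14 still carries an editing note. That makes it possible that further items would have been fielded. However, Appendix A is presented as the text going into REDCap, and the documents give no other version.

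A reader might also infer that recall bias undermines a planned before/after health comparison, because "how would you rate your health BEFORE starting this study" is asked only at exit, after about six months of unblinded device use, and question 4 anticipates disappointment with the assignment. The documents do not support this as a flaw in a planned analysis: no aim, endpoint or statistical section uses the change from question 9 to question 10. It matters only if someone decides to report that change.

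**Conclusion.** The point holds as a mismatch between stated aims and the instrument. Empowerment has 0 of 16 items, satisfaction with digital services has 0 of 16, device satisfaction has one proxy (question 8), and engagement is reached only indirectly. The Aim 3c hypothesis therefore has no direct measure and lacks the response format its own process calls for. Aim 3b is partly covered. Behavior change and perception of the technology are partly covered.

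This rests on one assumption: that Appendix A is fielded as printed. The consequence is confined to secondary, qualitative aims of a pilot. The HbA1c analysis and the quantitative secondary analyses are untouched. It is worth correcting because it is cheap to correct before patients exit and cannot be properly corrected afterwards.

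**What to change.** Add to Appendix A, at least for the CGM group, 5-point Likert items on:

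- (a) feeling empowered to self-manage diabetes;
- (b) engagement in changing health behaviors;
- (c) satisfaction with the monitoring device;
- (d) satisfaction with the apps and digital monitoring services.

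State in the plan how each will be summarized, for example the distribution over the five categories. Asking (a) to (c) in both groups is optional; Aims 3b and 3c concern CGM patients and do not require a comparison by arm.

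The cost is about a minute more of each patient's time and a survey-wording amendment. If the sponsor prefers not to change the survey, the minimum alternative is to reword the Aim 3b and 3c hypotheses and the endpoint examples to match what questions 5-8 measure. That gives up the empowerment question.

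Optional and subsidiary: if a before/after change in self-rated health is to be reported, ask question 9 at enrollment, before the randomization envelope is opened. Section 3.0 has the envelope handed over at consent, so the order within that visit matters. Otherwise, describe question 9 as a recalled rating.
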